#### **Confidentiality Statement**

Final 2.0 Amendment 1.0, 22-May-2017

Page 57 of 106

Related to PMI\_RD\_WKI\_000759

the normal range for vital signs can be repeated by clinical staff and judged by the Principal Investigator or designee to be not clinically significant for study participation.

## 7.2.1 Demographic Data

See Appendix A - Schedule of Events for the timepoints of assessment. Demographic data (sex, age, and ethnicity) will be recorded.

## 7.2.2 Identification of the Current Cigarette Brand

Information on the current cigarette brand will be collected in the smoking history.

7.2.3 Questions on Smoking History/Habits and Intention to Quit Smoking.

Study participants will be asked the following questions about their smoking history and habits:

- 1. Have you ever smoked 100 cigarettes or more in your life) (yes/no) If answer is Yes, move to question 2. If answer is No, move to question 8.
- 2. What brand of cigarettes do you smoke (free text)
- 3. Are you planning to quit smoking in the next 3 months? (yes/no)
- 4. Have you smoked at least 20 cigarettes per day for at least the past 5 consecutive years? (yes/no)
- 5. How many years have you smoked cigarettes in your entire life? (numeric response, 2 digits)
  - a. On average, how many cigarettes per day have you smoked during these years? (numeric response, 2 digits)
- 6. When you smoke cigarettes, do you mostly exhale smoke through the nose? (yes/no)
- 7. Have you used any of the following tobacco/nicotine containing products over the last 3 months?

	Yes	No
a. E-cigarette		
b. Cigar		

## **Confidentiality Statement**

Data and information contained in this document are considered to constitute trade secrets and confidential commercial information, and the legal protections provided to such trade secrets and confidential information are hereby claimed under the provisions of applicable law. No part of this document may be publicly disclosed without the written consent of Philip Morris Products S.A.

Confidential

P1-CMS-01-US

Final 2.0 Amendment 1.0, 22-May-2017

Page 58 of 106

Related to PMI\_RD\_WKI\_000759 CSP

c. Pipe or Hookah	
d. Snuff or chewing tobacco	
a. Nicotine products to help you quit smoking (patch, gum,)	
a. Other	

- 8. Have you smoked any cigarettes in the past 3 years? (yes/no)
- 9. Have you used any of the following tobacco/nicotine containing products over the last 3 years?

	Yes	No
a. E-cigarette		
b. Cigar		
c. Pipe or Hookah		
d. Snuff or chewing tobacco		
a. Nicotine products to help you quit smoking (patch, gum,)		
a. Other		

This self-reported cigarette daily consumption will be used to assess eligibility.

## 7.2.4 Medical History, Concomitant Disease, Previous and Ongoing Medications

Relevant medical history will be documented at the Screening Visit. Medical history is defined as any condition that started and ended prior to the Screening Visit. Any concomitant disease will be documented at the Screening Visit. A concomitant disease is defined as any condition that started before and was going on at the time of ICF signature.

All medication taken 30 days prior to Visit 1 and all concomitant medication taken during the study will be documented in the source documentation and recorded in the CRF. Medication which was started prior to Visit 1 and which is still being taken by the study participant during the study as well as medication that is initiated after Visit 1 will be considered as a concomitant

#### **Confidentiality Statement**

Philip Morris Products SA

Clinical Study Protocol

Confidential

P1-CMS-01-US

Final 2.0 Amendment 1.0, 22-May-2017

Page 59 of 106

Related to PMI\_RD\_WKI\_000759

medication. Medication initiated after Visit 1 is also referred to as concomitant medication. This applies to both prescription and over-the-counter products.

Records of medication taken include the drug name (preferably both generic and trade name), route of administration (*e.g.*, oral, intravenous), total daily dose/unit (*e.g.*, expressed in mg, mL or international units, IU), indication, the start and if applicable, the stop date (day, month and year). Any therapy changes (including changes of regimen) during the study have to be documented. Any concomitant medication that is still being taken by the study participant at the EOS will be recorded in the CRF.

[figure not shown]
7.2.5 Brief physical examination and nasal and throat exam.

See Appendix A - Schedule of Events for the timepoints of assessment. A brief physical examination (including an examination of the head and neck, chest, heart (cardiovascular) and abdomen), and a nasal and throat exam, will be performed at Screening and at study discharge or at early termination. Additional physical examinations may be performed throughout the study as judged by the Principal Investigator or designee.

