**Clinical Study Protocol** 

Confidential

P1-CMS-01-US

Final 2.0 Amendment 1.0, 22-May-2017

Page 41 of 106

Related to PMI\_RD\_WKI\_000759

test performed immediately after smoking (5-10 minutes post T0). T0 will be defined as the start of cigarette smoking for smokers (time point of first product use during study day). T0 should be the same for all smokers within an acceptable time window of 1 hour. Never smokers will also have the STT test performed in the morning at 8 am  $\pm$  30 minutes (designated T0 $\pm$  30 minutes). All study participants (smokers and never smokers) will then have the STT test performed until 4h30 min), 8h (may be performed until 8h30 min), and 12h (may be performed until 12h30 min) post T0, ensuring at least approximately 4 hours between the beginning of each STT test. The participant will be asked to confirm he can no longer feel the sweet taste. Study participants will drink a glass of water (approximately 240 mL) before STT tests are performed.

Samples for plasma nicotine assessment will be collected at approximately the same time points that STT test is performed at  $T_0$ , 4h (may be performed until 4h30 min), 8h (may be performed until 8h30 min), and 12h (may be performed until 12h30 min) post  $T_0$ .

Nasal scraping of the inferior turbinate of both nostrils will be performed on all 14 study participants at the end of Visit 3, after all other clinic assessments, except the brief physical examination which will be done after the nasal scraping:

- For 4 study participants, the nasal scraping (left nostril with method 1, right with method 2) will be performed and samples collected for subsequent histological assessment.
- For the 10 remaining study participants, 5 will undergo nasal scraping using method 1, and 5 using method 2. For all 10 study participants, cells from one nostril will be added into one buffer, cells from the other nostril into a second buffer. Samples will be collected for subsequent RNA quantity and quality analysis.

Full procedure is described in the "Method establishment to obtain human nasal epithelial sample using the Rhino-probe".

Upon conclusion of all clinic assessments, at the time of discharge on Visit 3, the Principal Investigator or designee will perform a brief physical examination on the study participant.

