# **5.2** Discontinuation of Study participants from the Study

Discontinued study participants will include both study participants who withdraw from the study (study participant's decision) or study participants who are removed from the study by the Principal Investigator. A study participant can only be discontinued from the study after enrollment.

Study participants will be informed that they are free to withdraw from the study at any time. Study participants should be questioned for the reason of premature withdrawal from the study, although they are not obliged to disclose it. This needs to be fully documented in the source document and case report form (CRF).

If the study participant withdraws his consent for the study, the Principal Investigator or designee needs to document if:

- The study participants agrees that the data can be used until the time of withdrawal.
- The study participant agrees to have his samples collected until the time of withdrawal to be analyzed.

This information needs to be fully documented in the source document and CRF.

When a study participant is discontinued from the study, he will be asked to perform the examination procedure planned in Section 9.4 as soon as possible after the time of discontinuation, unless the study participant is not willing to perform any additional assessment.

Study participants discontinued from the study cannot re-enter the study.

Study participants must be discontinued from the study for any of the following reasons:

- Withdrawal of informed consent.
- Any AE or condition (including clinically relevant changes in a laboratory parameter) which at the discretion of the Principal Investigator no longer justifies the study participant's participation in this study.
- The Sponsor or the Principal Investigator terminates the study. If the Sponsor or the Principal Investigator decides to prematurely terminate the study, the study participant

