# 8.4 Adverse Events Leading to Discontinuation

Study participants will be advised they are free to withdraw from the study at any time. Over the course of the study, the Investigator and/or the Sponsor may discontinue participation of any study participant from the study in the case of unnecessary risk, adverse events, or noncompliance. When a study participant withdraws or is discontinued from the study, all safety data normally required at the end of the study will be obtained, if possible.

Subjects who are discontinued from the study because of an AE will undergo the early termination procedures as soon as practical after the day of discontinuation and will enter the period of safety follow-up. Any AEs or SAEs that are ongoing at the end of the Safety Follow-up Period will be managed as described in section 8.2.2.

If, in the opinion of the Investigator, Sponsor, or the IRB, the incidence and severity of AE(s) outweighs the benefit of continuing the study, the study may be terminated. In the event this course of action is to be pursued, the Investigator will make every attempt to communicate

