## **Confidentiality Statement**

Data and information contained in this document are considered to constitute trade secrets and confidential commercial information, and the legal protections provided to such trade secrets and confidential information are hereby claimed under the provisions of applicable law. No part of this document may be publicly disclosed without the written consent of Philip Morris Products S.A.

Philip Morris Products SA

Clinical Study Protocol

Confidential

P1-CMS-01-US

Final 2.0 Amendment 1.0, 22-May-2017

Page 77 of 106

Related to PMI\_RD\_WKI\_000759

participant will be asked to confirm he/she can no longer feel the sweet taste. Study participants will drink a glass of water (approximately 240 mL) before STT tests are performed.

Samples for plasma nicotine assessment will be collected at approximately the same time points that STT test is performed at  $T_0$ , 4h (may be performed until 4h30 min), 8h (may be performed until 8h30 min), and 12h (may be performed until 12h30 min) post  $T_0$ .

Nasal scraping of the inferior turbinate of both nostrils will be performed on all 14 study participants at the end of Visit 3, after all other clinic assessments, following the "Method establishment to obtain human nasal epithelial sample using the Rhino-probe".

Full procedure will be described in the "Method establishment to obtain human nasal epithelial sample using the Rhino-probe". Upon conclusion of all clinic assessments, at the time of Discharge on Visit 3, the Principal Investigator or designee will perform a brief physical examination on the study participant.

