# **9.4** Early Termination Procedures

If a study participant is discontinued from the study prematurely the following assessments will be performed (unless the subject refuses to do so):

- Adverse event recording
- Hematology
- Clinical chemistry
- Urine analysis
- Vital signs
- Brief physical examination.

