## **Appendix A - Schedule of Events**

	Visit 1	Visit 2	Visit 3	Follow-Up
Study day	D-30 to D-1	D1	D2	D3
Informed consent	1			
Review study procedures	1	1	1	
Assessment/review of inclusion/exclusion criteria	1	1		
Demographics	1			
Body height, weight and derived BMI	1			
Medical history and concomitant disease	1			
Hematology, clinical chemistry, urine analysis	1		1 (at discharge)	
Smoking history	1	1		
Readiness to comply to study procedures, incl. smoking interruptions	1	1		
Prior and concomitant medication assessment	1	1	1	
Vital signs	1	1	1	
Nasal and throat exam	1	1		
Brief physical exam	1		1 (at discharge)	
Spirometry post-bronchodilator	1			
Serology for HIV, hepatitis B and C	1			
Alcohol breath test	1	1		

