#### **Confidentiality Statement**

CSP

P1-CMS-01-US

Final 2.0 Amendment 1.0, 22-May-2017

Page 99 of 106

Related to PMI\_RD\_WKI\_000759

	Visit 1	Visit 2	Visit 3	Follow-Up
Drug screening	1	1		
Exhaled carbon monoxide	1	1		
Skin Prick Test	1			
Urine Cotinine	1	1		
Enrolled		1		
Plasma nicotine sampling			1 a	
Saccharin transit time test	1	1	1 a	
Nasal scraping			1 b,c	
Discharge from Study			1 d	
Adverse event recording	1	1	1	1
a At time: $T_0$ (post-cigarette), 4h (may be performed un post- $T_0$ . For the never smokers equivalent time points v	vill be used.	med until 8h30 min), and	12h (may be performed	l until 12h30 min)
b After the last STT test and collection of sample for pla c Collection of samples for subsequent histological asse d Upon completion of all study assessments		quantity and quality.		

d Upon completion of all study assessments.

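### The nasal and throat exam, a listed safety endpoint, is required at discharge by section 7.2.5 but scheduled only before nasal scraping in Appendix A, and the SAP does not report it

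*Protocol*

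**What the plan says.** The nasal and throat exam is one of the safety endpoints under the second secondary objective (protocol synopsis and section 3.2; SAP section 2.2).

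- **Section 7.2.5** sends the reader to Appendix A for timing. It then states that the brief physical examination, "and a nasal and throat exam, will be performed at Screening and at study discharge or at early termination".
- **Appendix A** has a row "Nasal and throat exam" marked at Visit 1 and Visit 2, with Visit 3 and Follow-Up empty. The brief physical exam has its own row, marked at Visit 1 and, with a note for discharge, at Visit 3. Footnote d, on the study discharge row, reads "Upon completion of all study assessments".
- **Synopsis and section 4.1** place scraping of both nostrils at the end of Visit 3, "after all other clinic assessments, except the brief physical examination which will be done after the nasal scraping".
- **Section 9.2** says "Upon conclusion of all clinic assessments, at the time of Discharge on Visit 3" a brief physical examination is done. It names no other exam, and neither do the matching sentences in the synopsis and section 4.1.
- **Early termination:** under section 5.2 a discontinued participant "he will be asked to perform the examination procedure planned in Section 9.4". The section 9.4 list ends with "Brief physical examination" and does not contain the nasal and throat exam. Section 8.4 adds that, on withdrawal or discontinuation, "all safety data normally required at the end of the study will be obtained, if possible".
- **SAP section 5.5.4.2** covers vital signs, adverse events, laboratory parameters and serology. It says nothing about the nasal and throat exam.

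**The concern.** Section 7.2.5 and the schedule it relies on give different timepoints for the same exam. A site working from the Schedule of Events would omit an exam that the procedures section requires. The omitted exam is the one that could show what scraping did to the nose. The two scheduled exams serve eligibility (exclusion criterion 4) and take place before any scraping, so they cannot record a local effect of it. Standardising the scraping procedure with two methods is itself a secondary objective, which makes local findings after scraping relevant.

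There is also a compliance problem. Section 11.1.2 counts assessments not performed as protocol deviations, so a site that follows Appendix A exactly still departs from section 7.2.5. Finally, results of the clinical assessments go into the CRF under section 7.2, but the SAP has no place to report these.

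**Working it through.** The plan states no figure for this point, so the check compares the texts and counts.

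**Is the blank Visit 3 cell real?** The neighbouring brief physical exam row keeps its empty Visit 2 cell and its discharge note, so the columns read correctly. Exclusion criterion 4 separately supports exams at Visits 1 and 2. The discharge sentences in the synopsis, 4.1 and 9.2 also leave the exam out. The blank is therefore in the plan and is not an effect of text extraction.

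**Timepoints side by side** (n = 14 enrolled, no replacement):

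| Source | Visit 1 | Visit 2 | Discharge or early termination | Planned exams |
|---|---|---|---|---|
| Section 7.2.5 | yes | not mentioned | yes | 14 + 14 = 28 |
| Appendix A | yes | yes | no | 14 + 14 = 28 |
| Common to both | yes | – | – | 14 |
| Needed to satisfy both | yes | yes | yes | 14 × 3 = 42 |

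The totals agree at 28, but only the 14 Visit 1 exams are the same.

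**Exams after scraping.** Scraping comes at the end of Visit 3.
- Under Appendix A, both exams precede it: 0 of 14 participants have a scheduled exam afterwards.
- Under section 7.2.5, the order has to be inferred. Footnote d puts discharge after all assessments, so an exam at discharge would follow scraping for completers, up to 14 of 14. The synopsis and 4.1, however, exempt only the brief physical examination from preceding scraping. The order is therefore not settled.

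**Early termination.** Section 9.4 lists six items: adverse event recording, hematology, clinical chemistry, urine analysis, vital signs and brief physical examination. The nasal and throat exam is 0 of 6, although 7.2.5 requires it. Section 8.4 does not resolve this, because the schedule does not place this exam at the end of the study.

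**SAP outputs.** 16 tables + 4 figures + 15 listings = 35. Outputs for the nasal and throat exam: 0 of 35. Tables A 11 and A 12 and Listing 13 would show only those findings that were recorded as adverse events.

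**The case against.** The strongest reply is that section 7.2.5 is the outlier. The synopsis, 4.1, 9.2, 9.4 and Appendix A all give only the brief physical examination at discharge or termination, and 7.2.5 itself defers to Appendix A. The simpler correction would then be to change 7.2.5 to Visits 1 and 2. The only text that orders assessments against scraping could also be read to place a discharge-day nasal exam before it, so a lost exam of the scraped site does not strictly follow from the mismatch.

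On safety, a physical examination that includes the head and neck follows scraping. Adverse events are queried before release, and new untoward findings must be recorded as adverse events. There is a day of follow-up, with a telephone call for ongoing events, and the investigator may add physical examinations. Section 2.3.2 rates the procedural risk as comparable to routine examinations. Participants who stop early will almost always not have been scraped. The separate Rhino-probe method document, and Figure 1, might specify an inspection after scraping.

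Much of this stands. The order is unstated, safety is partly covered, the early termination omission carries little scraping-related risk, and the method document cannot be checked. None of it tells the site which instruction to follow or supplies the missing SAP output. The protocol treats this exam as separate from the brief physical examination, with its own schedule row and endpoint line. Reducing 7.2.5 to Visits 1 and 2 would remove the conflict but leave a safety endpoint that cannot show any effect of scraping.

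**Conclusion.** The concern holds. Section 7.2.5 conflicts with Appendix A and with section 9.4, and the SAP reports nothing for an endpoint it lists. Under the schedule as written, 0 of 14 participants have a scheduled dedicated nasal and throat exam after scraping, 0 of 6 early termination items is this exam, and 0 of 35 SAP outputs cover it.

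Confidence is high for the textual conflict. It is lower for the size of the safety gap, because the order relative to scraping is not stated and the Rhino-probe document is not available. What would be lost is the dedicated exam of the scraped site and the reporting of its findings; general adverse event surveillance remains. The STT, nicotine and RNA results are unaffected. The plan should be corrected, but nothing here threatens the primary objectives.

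**What to change.** 1. In Appendix A, mark the nasal and throat exam at Visit 3, at discharge and after scraping.
2. Add the exam to the section 9.4 list and to the discharge sentences in the synopsis, 4.1 and 9.2.
3. In the synopsis and 4.1, extend the exception for assessments done after scraping to cover both the brief physical examination and the nasal and throat exam. Add the same exception to 9.2, which has none.
4. In the SAP, add one by-subject, by-visit listing of nasal and throat exam and brief physical exam findings for the safety population, and cite it in 5.5.4.2.

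Naming Visit 2 in section 7.2.5 is optional, since Appendix A and exclusion criterion 4 already state it.

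The cost is wording edits in five protocol places (synopsis, 4.1, 9.2, 9.4 and Appendix A), one SAP listing, and one short exam per participant at discharge. I assume a few minutes each; the documents give no duration. Section 7.2.5 already requires the exam. Because it would follow the STT tests, nicotine sampling and scraping, it cannot affect those data.

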# 7.2.6 Body Height and Weight

See Appendix A - Schedule of Events for the timepoints of assessment. Body weight and height will be measured.

Body mass index (BMI) will be calculated from the body weight and height using the following formula:

At Visit 1, BMI will be calculated from the height and weight recorded at Visit 1.

# 7.2.7 Vital Signs

See Appendix A - Schedule of Events for the timepoints of assessment. Systolic and diastolic blood pressure, pulse rate and respiratory rate will be measured at each visit. All measurements will be made according to the latest version of SOP titled *Vital Signs Measurement*.

## 7.2.8 Other Clinical Assessments

## 7.2.8.1 Spirometry post-bronchodilator

See Appendix A - Schedule of Events for the timepoints of assessment.

Spirometry post-bronchodilator testing is mandatory during the screening for all study participants.

Spirometry post-bronchodilator testing will be performed in accordance with the latest version of SOP titled *Spirometry*, latest version of SOP titled *Reversibility testing* and also according to the American Thoracic Society (ATS) recommendations. (Miller et al., 2005)

## Bronchodilator Dosing

- 1. Bronchodilator dosing should be performed after baseline spirometry has been completed following latest version of SOP and also according to the ATS recommendations. (Miller et al., 2005)
- The chosen bronchodilator will be Salbutamol and the selected dose will be 90 µg by using a metered dose inhaler (MDI). The MDI should be primed according to the manufacturer's instructions.

## **Confidentiality Statement**

Related to PMI\_RD\_WKI\_000759

- 3. Four separate doses (one puff) of the inhaled bronchodilator will be administered by MDI in one long, slow breath to total lung capacity (TLC).
- 4. The doses should occur approximately 30 seconds apart using a spacer.
- 5. Each inhaled dose of the inhaled bronchodilator should be held by the study participant for 5-10 seconds.

10 to 15 minutes after the inhaled bronchodilator is given, spirometry maneuvers should be initiated following latest version of SOP CO-038 and also according to the ATS recommendations. (Miller et al., 2005).

The doses, the number of sprays administered and the interval period between administration of the bronchodilator and the assessment, will be recorded on dedicated log.

